## **7.6.2 Nonabsorbable Dye Marker**

The dye marker FD&C Blue #2, also named Indigo carmine or Indigotin, will be supplied in accordance with current Good Manufacturing Practices (cGMP).

### **7.6.2.1 Shipment, Receipt, and Storage and Dispensing**

The dye marker will be supplied. The dye makers must be stored in a secured limited-access area and maintained at room temperature  $\leq 25^{\circ}\text{C}$  and will not require temperature monitoring during shipment.

## 8. TIMING OF STUDY PROCEDURES

Patients will provide written informed consent before any study-related procedures are performed.

The study Schedule of Assessments is included in [Section 7.1.1 \(Table 1\)](#).

### 8.1 Screening Period

Throughout the screening period, patients are to remain on their prestudy porcine PERT.

#### Visit 1, D-21 to D1: Screening Visit

The following procedures will be performed at the Screening Visit (which may take place over more than one day):

- Obtain signed informed consent from the patient before any study-related assessments are made
- Collect relevant medical history, including concomitant illnesses/diseases, previous/concomitant medications, and record AEs
- Complete physical
- Specific CF assessment including a pulmonary function test by spirometry to determine FEV1 >30% of predicted normal for age, sex, and height at screening
- Record body height and weight
- Record vital signs while sitting (blood pressure, pulse rate, breathing rate, and temperature)
- Assess for eligibility (against the inclusion and exclusion criteria)
- Record demographic data such as ethnic origin, date of birth, and sex
- Collect urine sample for urinalysis
- Perform a serum pregnancy test, if applicable
- Collect samples for hematology, clinical chemistry, PT/INR, activated partial thromboplastin time (aPTT)
- Collect blood samples for vitamin determination (A, D, E, and K)

- Patients will be required to fast for at least 8 hours before the collection of screening laboratory tests (insulin dependent diabetics may be excluded from fasting).
- Collect samples for fasting lipids
- Obtain a stool sample for fecal pancreatic elastase concentration in the selected central laboratory

### **Visit 2 Telephone (T)**

Once patient eligibility is confirmed, patients will be contacted by telephone and instructed to:

- Refrain from alcohol consumption for 24 hours before the visit
- Bring their prestudy porcine PERT with them to the clinic in the event they are randomized to their prestudy PERT

## **8.2 First Treatment Period (Visits 3, 4 (T), 5 (T), and 6)**

### **Visit 3 (Day 1): Randomization Visit - Must Occur Within 21 Days of Visit 1**

During the first treatment period, patients will be randomized to either a fixed dose of MS1819 or to their prestudy porcine PERT. Visit 3 will take place if the patient is eligible to continue on the basis of data obtained at the Screening visit. The following procedures will be performed:

- Review Inclusion /Exclusion Criteria
  - Focused physical exam to evaluate gastrointestinal tract, heart, and lungs
  - Record body height and weight
  - Record vital signs while sitting (blood pressure, pulse rate, breathing rate, and temperature)
  - Collect urine sample for urinalysis
  - Perform a urine pregnancy test (urine dip stick), if applicable
  - Assess and record malabsorption signs and symptoms
  - Record any changes in AEs and concomitant medication
-

- 
- Randomization to either a fixed dose of MS1819 or to continue their prestudy porcine PERT
  - Instruct patients on use and dosing
  - Instruct/dispense study drug to patient (if randomized to MS1819), otherwise patients are to continue on their prestudy porcine PERT. For patients randomized to MS1819, instructions will vary depending on the dose to which the subject is randomized (either 2240 or 4480 mg/day)

#### **V4 (T) (Day 8 ± 2) and V5 (T) (Day 15 ± 2)**

The following procedures will be performed:

- Record any changes in AEs and concomitant medication review.
- Assess and record malabsorption signs and symptoms
- Confirm patient scheduled date for V6 (first stool collection in supervised controlled setting) and remind patients to come in fasted status.

#### **Visit 6: Stool Collection in Controlled Supervised Facility (Day 17 + 5)**

Patients will be admitted for a maximum of 7 days to a facility providing supervised confinement for collection of stool for determination of CFA, CNA, and stool weight. The timing of the previous visits (Visit 1 and Visit 2) should be made with the aim of accommodating the patients' schedules for the supervised confinement. To accommodate patients' schedules for the supervised confinement, a +5 day visit window is permitted.

- During the third week (Visit 6) (+5 days), patients will undergo admission to a controlled supervised facility for stool collection to support the CFA and CNA assessment and weight. A +5 day visit window is allowed to accommodate investigative site staff and patients' schedules for the supervised confinement.
- After appearance of fecal stool dye markers has been measured, patients CFA and CNA will be measured under their dose of MS1819 or prestudy dose of porcine PERT using standardized high-fat meals during the 3-day standardized diet. Additional detailed information provided in the study operations manual should be followed.
- The CFA calculation will be based on the measured fecal fat content in relation to ingested fat quantities during the 3-day stool collection period.

After completion of the initial treatment period during the completion of V6, patients will be instructed to switch their study medication to either a fixed dose of MS1819 or their prestudy porcine PERT. The stool collection and dietary procedures will be conducted as described in Section 8.3.3.1. (Instructions for Supervised Confinement)

The following procedures will be performed at Visit 6:

- Begin 72-hour controlled diet
- Focused physical exam to evaluate gastrointestinal tract, heart, and lungs
- Record body height and weight
- Record vital signs while sitting (blood pressure, pulse rate, breathing rate, and temperature)
- Record any changes in AEs and concomitant medication
- Instruct/dispense study drug
- Assess and record malabsorption signs and symptoms
- Marker-to-marker stool collection and stool weight (central laboratory will weigh the stool that is collected)
- Collect urine sample for urinalysis
- Perform a urine pregnancy test (urine dip stick), if applicable
- Collect samples for hematology, clinical chemistry, PT/INR, and aPTT
- Collect samples for fasting lipids after patients have been in a fasting status for at least 8 hours (insulin dependent diabetics may be excluded from fasting).
- Collect blood samples for vitamin determination (A, D, E, and K)
- Collect a serum sample for circulating anti-LIP2 lipase antibodies and MS1819 concentrations
- Record all fat, protein, and dose of study drug taken with every meal and snack during the confinement period
- Verify study drug count on the last day of confinement
- Return MS1819 (only for patients originally randomized to MS1819) on the last day of confinement

At the end of the supervised confinement (once the second blue dye marker sample has been collected), patients will crossover to their new treatment. Patients originally randomized to MS1819 will begin treatment on their prestudy porcine PERT. Patients originally randomized to their prestudy porcine PERT will begin treatment on MS1819 (at either a dose of 2240 or 4480 mg/day).

### **8.3 Second Treatment Period (Visits 7 [T], 8 [T] and 9)**

The second treatment period will begin once patients have passed their second blue dye marker at the end of V6, and the stool sample collection is complete. As soon as this has occurred, patients will crossover to their new treatment (either MS1819 or patient's prestudy porcine PERT).

#### **V7 (T) (Day 29 ± 2) and V8 (T) (Day 36 ± 2)**

The following procedures will be performed:

- Record any changes in AEs and concomitant medication review.
- Assess and record malabsorption signs and symptoms
- Confirm patient scheduled date for V9 (second stool collection in supervised controlled setting) and remind patients to come in fasted status.

#### **Visit 9: Stool Collection in Controlled Supervised Facility (Day 38 +5)**

Patients will be admitted for a maximum of 7 days to a facility providing supervised confinement for collection of stools for determination of CFA, CNA and stool weight. Dosing must have occurred for at least 16 days prior to the start of the scheduled confinement. The stool collection and dietary procedures will be conducted as described in Section [8.3.3.1](#) (Instructions for Supervised Confinement). The following procedures will be performed at Visit 9:

- Begin 72-hour controlled diet
  - Focused physical exam to evaluate gastrointestinal tract, heart, and lungs
  - Record body height and weight
  - Record vital signs while sitting (blood pressure, pulse rate, breathing rate, and temperature)
  - Record any changes in AEs and concomitant medication
  - Instruct/dispense study drug
-

- Assess and record malabsorption signs and symptoms
- Marker-to-marker stool collection and stool weight (central laboratory will weigh the stool that is collected)
- Collect urine sample for urinalysis
- Perform a urine pregnancy test (urine dip stick), if applicable
- Collect samples for hematology, clinical chemistry, PT/INR, and aPTT
- Collect samples for fasting lipids after patients have been in a fasting status for at least 8 hours (insulin dependent diabetics may be excluded from fasting).
- Collect blood samples for vitamin determination (A, D, E, and K)
- Collect a serum sample for circulating anti-LIP2 lipase antibodies and MS1819 concentrations
- Verify study drug count on the last day of confinement
- Return MS1819 (only for patients that crossed over to MS1819) on the last day of confinement

At the end of the supervised confinement (once the second blue dye marker sample has been collected) all patients are to resume therapy on their prestudy porcine PERT. Patients who crossed over to MS1819 will resume treatment on their prestudy porcine PERT; patients who crossed over to their prestudy PERT will continue with their prescribed therapy. Remind patients of their scheduled Visit 10 date

### **8.3.3 Visit 10: End-of-Study /Early Withdrawal Visit (Day 56 ± 2)**

Patients will return to the clinic for their End of Study visit approximately 2 weeks after their last dose of study drug (either MS1819 or the patient's prestudy porcine PERT). In the event that patients do not complete V9, an Early Withdrawal visit will be held approximately 2 weeks after the last dose of study drug. The procedures scheduled for the End-of-Study visit are the same as those that should be conducted for the Early Withdrawal visit. The following procedures will be performed at the End-of-Study/Early Withdrawal Visit:

- Focused physical exam to evaluate gastrointestinal tract, heart, and lungs
  - Record any changes in AEs and concomitant medication
  - Assess and record malabsorption signs and symptoms
-

- Collect a serum sample for circulating anti-LIP2 lipase antibodies and MS1819 concentrations
- Collect blood samples for vitamin determination (A, D, E, and K)
- Perform a urine pregnancy test (urine dip stick), if applicable

### **8.3.3.1 Instructions for Supervised Confinement for V6 and V9**

Dosing must have occurred for at least 16 days prior to the supervised confinements. Beginning at breakfast (the first meal) on Day 1 of the supervised confinement, patients will be placed on a 72-hour controlled diet, with 100 g fat/day (3 meals and 2 snacks per day) and a minimum of 1.5 to 2 g of protein per kg of body weight. Although it is preferred to have the patient consume exactly 100 g of fat per day, the fat excretion assay remains valid with a fat intake range within 15% of the goal (i.e., 85 to 115 g of fat per day). The nutritional planning and calculation of dietary fat and nitrogen (protein) intake will be conducted by a qualified dietician at each site. The actual fat and nitrogen (protein) intake will be calculated from the recorded type and amount of food consumed. A central laboratory will calculate CFA, CNA, and stool weight values on the basis of dietary intake and the fat and nitrogen excreted in stool.

An indicator marker (500 mg of Food, Drug, and Cosmetics [FD&C] Blue #2) will be provided as two 250-mg capsules. The first marker (consisting of two 250-mg capsules) will be given at the beginning of breakfast or first meal on Day 1 of the supervised confinement to mark the start of the controlled diet. The second marker (two 250-mg capsules) will be given at the beginning of breakfast or first meal on Day 4 to mark the end of the controlled diet. Stool collection for fecal fat and nitrogen assessments must begin after the first marker has passed (the first stool containing the first marker is discarded) and is completed when the second marker has passed (the first stool containing the second marker is collected). Patients must continue the supervised confinement until the second stool marker is passed. The controlled diet will be maintained until the patient takes the second marker. Although it is not part of the controlled diet, the breakfast or first meal consumed on Day 4 of the supervised confinement should mimic (as closely as possible) the breakfast or first meal consumed on Day 1 of the supervised confinement.

If the patient has not passed the first blue dye marker within 4 days after ingesting the first dye marker capsules, or within 2 days after ingesting the second dye marker capsules, then 5-10 mg of oral bisacodyl may be given. Bisacodyl is the only laxative that may be given during the marker-to-marker stool collection period. Note: Patients on a stable chronic osmotic laxative may continue this therapy during the marker-to-marker stool collection.

The supervised confinement may take place within an inpatient facility or within an alternative confinement setting. This will be discussed and approved on an individual case basis by the sponsor. The alternative confinement setting will require the supervision of trained study site staff to oversee the study procedures.

## 9. SAFETY ASSESSMENTS

The planned Schedule of Assessments is included in [Section 7.1.1 \(Table 1\)](#).

### 9.1 Definitions

#### 9.1.1 Adverse Event

An AE is any untoward medical occurrence experienced by a patient in a clinical investigation; it does not necessarily have a causal relationship with this study drug. An AE can therefore be any unfavorable and unintended sign, symptom, or disease temporally associated with the use of a medicinal product, whether or not considered related to the medicinal product.

Active or worsening of EPI is not considered an AE for the purposes of this study. Worsening of EPI disease should not be recorded as an AE but should be recorded in the appropriate EPI CRF.

Adverse events may also include postdose complications that occur as a result of protocol-mandated procedures (e.g., invasive procedures such as venipuncture, biopsy, etc.). Preexisting events that increase in severity or change in nature during, or as a consequence of, use of a medicinal product in a human clinical study will also be considered AEs. Any preexisting medical condition or diagnosis associated with a clinically significant laboratory abnormality should be documented on the CRF or eCRF. The Investigator should attempt to establish a diagnosis of the event based on signs, symptoms, and other clinical information. In such cases, the unifying diagnosis should be documented as the AE, rather than the individual signs and symptoms (e.g., runny nose, scratch throat, cough, and low grade fever should be recorded as an upper respiratory infection and not each of the individual symptoms).

An AE does NOT include the following:

- Medical or surgical procedures (e.g., surgery, endoscopy, tooth extraction, transfusion); the condition that necessitates the procedure is an AE
- Any preexisting disease or condition or laboratory abnormality present or detected before the start of administration of study medication that does not worsen
- Laboratory abnormalities without clinical manifestations, which do not require medical intervention, or that do not result in termination or delay of study medication

- 
- Situations where an untoward medical occurrence has not occurred (e.g., hospitalization for elective surgery, social, or convenience admissions)
  - Overdose of any study drug or concomitant medication without any signs or symptoms, unless the patient is hospitalized for observation
  - Worsening and/or flares of EPI disease activity. This should be recorded in the appropriate EPI CRF. However, if disease worsening meets any of the criteria for an SAE, it must be recorded on the SAE form and reported to the Sponsor or designee within 24 hours of becoming aware of the event.

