#### **Criteria for Evaluation**

##### **Safety endpoints:**

AEs, SAEs, discontinuations due to adverse events, and laboratory values.

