### **5.6.2 MS1819/16/01 Phase 2a Study with MS1819**

An open-label, dose escalation Phase 2a study (MS1819/16/01) was conducted to investigate the safety of escalating doses of MS1819 in 11 patients with EPI caused by chronic pancreatitis or pancreatectomy.

The primary objective of this study was to investigate the safety of escalating doses of MS1819 (280 mg/day, 560 mg/day, 1120 mg/day, and 2240 mg/day). Each dose was given over a two-week period. A CFA was obtained at baseline after washout, and after each escalating dose period. Safety assessments included immunoallergic side effects, digestive symptoms, and clinical laboratory tests. The secondary objective of this study was to investigate the efficacy of MS1819 by assessment of CFA.

Eleven patients were enrolled into the study, and ten completed all doses. One patient withdrew during the 1120 mg/day dose level due to severe diarrhea. This was not assessed as related to study drug.

In the Intent-to-Treat population, mean CFA rose from a baseline of 46.1% to 62.4% at the highest dose ( $p = 0.001$ ). A number of symptoms improved comparing the highest dose to baseline, including stool consistency ( $p < 0.001$ ), number of bowel movements ( $p = 0.006$ ), steatorrhea ( $p = 0.008$ ), and abdominal pain ( $p = 0.148$ ). The treatment was well tolerated, with only two SAEs reported. Only one SAE was considered by the investigator to be possibly related to study drug, which was a patient with mild, transient elevations of liver enzymes. The elevations were between 2 and 3 X upper limit of normal (ULN), and lasted for about two weeks, a period of time that the patient was no longer receiving study drug. The patient had no symptoms of liver disease.

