### 7.2.3 Safety Endpoints

AEs, SAEs, safety lab values, and discontinuations due to adverse events.

In addition, laboratory test results will be summarized ([Section 15.2](#)):

- Hematology
- Biochemistry
- Fasting lipid profile
- Urinalysis
- Serum MS1819 concentrations
- Antibodies against LIP2 lipase

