## **9.7 Hepatic Monitoring**

The following guidelines are provided for the management of serum transaminase elevations in patients with new, clinically meaningful increases in liver function tests occurring during the study. All cases of new (i.e., since screening) elevations in ALT or AST  $\geq 3$  times ULN or any questions concerning the management of a patient with elevated serum transaminases should be discussed with the study Medical Monitor.

---

---

Patients who experience a new (i.e., since screening) elevation in ALT or AST level to  $\geq 3 \times \text{ULN}$  OR total bilirubin  $\geq 1.5 \times \text{ULN}$  will have hepatic monitoring (ALT, AST, Bilirubin) until one of the following occurs:

- Withdrawal from study if elevation in ALT or AST level to  $\geq 3 \times \text{ULN}$  is associated with a rise in total serum bilirubin to  $\geq 2 \times \text{ULN}$  (without laboratory findings of cholestasis [elevated serum alkaline phosphatase  $\geq 2 \times \text{ULN}$ ])
- Withdrawal from study if elevation in ALT or AST level to  $\geq 5 \times \text{ULN}$  is associated with new or exacerbated gastrointestinal (GI) symptoms (i.e., nausea, vomiting, right upper quadrant pain, and/or jaundice) and other causes are not evident
- Withdrawal from the study if elevation in ALT or AST is  $\geq 10 \times \text{ULN}$  regardless of serum bilirubin level

Causes of acute elevation of transaminases should be considered and ruled out (e.g., viral hepatitis, concomitant medications).

Patients discontinued from study drug administration should resume porcine PERT therapy according to physician prescription.

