#### **8.4 Deaths, Serious Adverse Events, and Other Significant Adverse Events**

Treatment-emergent SAEs, TEAEs leading to study discontinuation, TEAEs resulting in death, treatment-emergent SAEs by relatedness, treatment-emergent SAEs leading to discontinuation, and treatment-emergent SAEs resulting in death will be summarized for all subjects in the safety population for each study phase. Summary tables will reflect a count and percentage of subjects experiencing at least 1 TEAE in each system organ class and preferred term within each AE subset (serious, leading to discontinuation, death). These summaries will be presented by treatment group and overall for each dose in the crossover phase and overall for each dose in the extension phase with percentages that

use the number of subjects in the safety population as the denominator. These tabular summaries will be sorted by descending frequency by system organ class and by preferred term in the MS1819 treatment group.

Adverse events leading to study discontinuation, AEs resulting in death, and SAEs will be presented in data listings for subjects in the safety population for each dose of the crossover phase and for each dose of the extension phase.

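### Read literally, the *or* in Protocol 9.1.1's laboratory exclusion means that a symptom-free abnormality that ends study drug is not an adverse event

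*Protocol*

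**What the plan says.** Protocol 9.1.1 introduces a list with "An AE does NOT include the following". One bullet in it reads "Laboratory abnormalities without clinical manifestations, which do not require medical intervention, or that do not result in termination or delay of study medication". The bullet on worsening pancreatic insufficiency in the same list carries an override: "However, if disease worsening meets any of the criteria for an SAE, it must be recorded on the SAE form". The laboratory bullet carries none.

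Protocol 9.7 gives three rules for withdrawal on liver tests. One is "Withdrawal from the study if elevation in ALT or AST is" at or above 10×ULN, whatever the bilirubin. Another combines ALT or AST at or above 3×ULN with bilirubin at or above 2×ULN, without laboratory evidence of cholestasis. The third, at or above 5×ULN, also requires gastrointestinal symptoms. Section 9.7 does not say that the elevation is to be recorded as an adverse event.

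The safety endpoints in the protocol synopsis are "AEs, SAEs, discontinuations due to adverse events, and laboratory values", and section 7.2.3 has "AEs, SAEs, safety lab values, and discontinuations due to adverse events". SAP 8.4 tabulates "TEAEs leading to study discontinuation". SAP 8.1 and 8.3 define treatment-emergent events as a subset of adverse events, and the SAP has no adverse event definition of its own.

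**The concern.** The bullet names three conditions: no clinical manifestations, no need for medical intervention, and no termination or delay of drug. Because the last is joined by *or*, they need not all hold. A patient with no symptoms and no treatment who is taken off drug for a liver value can meet the exclusion, yet this is a withdrawal the protocol itself requires.

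Two named safety endpoints are affected: adverse events, and discontinuations due to them. An event screened out at 9.1.1 gets none of the attributes that Protocol 9.2 asks the investigator to assign to adverse events (severity, relatedness, action taken), and it cannot reach SAP 8.4. If some sites read the bullet literally and others read it as probably intended, the same event is counted at one site and not at another. Protocol 11.5 applies section 9 to the extension phase as well.

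**Working it through.** No figure in the plan needs reproducing, because the point turns on wording. The check has four steps.

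**1. Three readings of the bullet.** Let S = symptoms present, I = medical intervention needed, T = drug terminated or delayed (1 = yes, 0 = no).

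- (a) Flat *or*: excluded if S = 0, or I = 0, or T = 0.
- (b) Nested: excluded if S = 0 and (I = 0 or T = 0).
- (c) Conjunctive: excluded only if S = 0 and I = 0 and T = 0.

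| S | I | T | (a) | (b) | (c) |
|---|---|---|---|---|---|
| 0 | 0 | 0 | excluded | excluded | excluded |
| 0 | 0 | 1 | excluded | excluded | AE |
| 0 | 1 | 0 | excluded | excluded | AE |
| 0 | 1 | 1 | excluded | AE | AE |
| 1 | 0 | 0 | excluded | AE | AE |
| 1 | 0 | 1 | excluded | AE | AE |
| 1 | 1 | 0 | excluded | AE | AE |
| 1 | 1 | 1 | AE | AE | AE |

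Reading (a) excludes 7 of 8 combinations, (b) excludes 3 and (c) excludes 1. The case at issue is the second row (S = 0, I = 0, T = 1). It is excluded under both readings that keep the *or*, and is an adverse event only under (c).

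**2. Does the protocol create that case?** Two of the three withdrawal rules in 9.7 have no symptom condition. The 10×ULN rule is the cleaner example, since a marked rise in bilirubin may itself cause symptoms. The rule at 5×ULN requires symptoms, so it falls outside the point under reading (b).

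**3. Is it caught elsewhere?**

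- *Disposition.* SAP 5.1 reports withdrawals with reasons, whether or not an adverse event is recorded. The removal reasons in Protocol 7.3.4 name no laboratory or hepatic criterion.
- *Crossover laboratory outputs.* SAP 8.5.1 summarises ALT and AST at or above 3×ULN and bilirubin at or above 1.5×ULN by treatment, at screening and at 3 weeks after first dose. An unscheduled peak may fall outside those times. Hepatic monitoring results are also listed.
- *Extension phase laboratory outputs.* SAP 8.5.2 gives descriptive statistics and listings, with no summary of elevations.
- *Serious events.* Protocol 9.1.2 lets an important medical event be reported as serious on medical judgement.

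The event therefore stays visible, but none of these routes restores it to the SAP 8.4 count.

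**4. Size of one missed case.** SAP 8.4 uses the safety population as denominator. Protocol 7.3.1 plans about 36 enrolled, and section 7.4.3 randomises 1:1 to the two doses.

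- Planned enrolment per dose: 36/2 = 18, so 1/18 = 5.6%.
- Completer target per dose: 15, so 1/15 = 6.7%.
- First extension cohort: 9, so 1/9 = 11.1%.

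Each figure is the effect of a single case. None is an expected frequency.

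**The case against.** The strongest reply is that reading (c) is plausible and probably intended. Naming termination or delay of drug makes most sense if such events were meant to count. The flat reading would even exclude symptomatic abnormalities, against the section's own opening definition of an adverse event. This stands. A reader might infer that withdrawals under 9.7 are definitely not adverse events, or that rates on MS1819 will be understated. The documents support neither as a certainty, only that the literal text allows both.

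Second, medical intervention is undefined. If the monitoring, the search for causes or the return to PERT that 9.7 calls for counted as intervention, reading (b) would keep the event as an adverse event. This narrows the point but does not remove it, because sites would still have to guess.

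Third, the withdrawal and the liver values are reported elsewhere, as shown above. This also stands: only the adverse event tables, and the attributes attached to them, are at risk.

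Fourth, a reader might take the earlier chronic pancreatitis study as evidence of a hepatic withdrawal rate. Its single possibly related serious event was "a patient with mild, transient elevations of liver enzymes", at 2 to 3×ULN. On the figures reported it met no withdrawal rule in 9.7, and it was captured as a serious event. Protocol 5.6.3 calls laboratory values in the first cystic fibrosis trial unremarkable, and section 11.2 reports no safety issues in the present study. The earlier case explains why liver enzymes are watched, but gives no rate.

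**Conclusion.** The bullet is wrong as written. Followed literally, it excludes a symptom-free, untreated laboratory abnormality that ends study drug, and no passage in either document overrides it. The consequence is possible inconsistent recording between sites, with possible undercounting of adverse events and of treatment-emergent events leading to discontinuation.

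One missed case amounts to about 5.6% of planned enrolment per crossover dose (6.7% of the completer target). This assumes equal allocation of about 36 patients and a site that applies the literal wording. The number of such cases is unknown and may be zero.

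Two stronger conclusions do not follow. The hepatic finding would not vanish from the report, since disposition and laboratory outputs would carry it. Nor are these counts primary safety endpoints: the documents call safety a primary objective and list the counts simply as safety endpoints.

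**What to change.** Reword the laboratory bullet in 9.1.1 so that the three conditions are joined by *and*: an abnormality is excluded only if it has no clinical manifestations, needs no medical intervention, and neither ends nor delays study drug. Add a sentence, cross-referred to 9.7, that any laboratory abnormality leading to withdrawal under that section is recorded as an adverse event with action taken, so that it reaches SAP 8.4 in both phases.

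This changes recording only and leaves every threshold and withdrawal rule as it is. The cost is one clause, one sentence and a memo to sites, and possibly a few more laboratory adverse events.
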